## Sample Size and Statistical Analysis

### Sample Size

The primary endpoint is the ARAT, the MCID for which is 5.7 points. This study is powered for the Aim 1 analyses, which will compare [1] patients receiving TR (i.e., combining TR+Sinemet with TR+placebo) to [2] patients receiving UC. Based on a randomization distribution of 3:3:2 (TR+Sinemet, TR+placebo, UC), and using a 2-sided alpha of 0.05, this study will have 80% power to detect a mean difference between groups of 5.7 points in the change in ARAT-time, assuming a SD of 7.4 points, with a total of 72 patients: 27 in TR+Sinemet, 27 in TR+placebo, and 18 in UC.

The study is funded to enroll 72 patients. Subject dropout may be as high as 20%, and so when possible additional patients may be enrolled.

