### Statistical Analysis

We will present descriptive statistics by group for the important covariates including age, site, time from stroke to randomization, MEP status, and hours of outside rehabilitation. We will also report compliance, defined as the percentage of the 36 sessions during which patients complete more than half ( $\geq 36$  min) of assigned activities. For all analyses, data not normally distributed will be appropriately transformed.

Primary efficacy analysis will use the Intent-To-Treat population, consisting of all randomized subjects and multiple imputation for missing data. Secondary analysis will examine the Per-Protocol population, defined as all subjects with complete data who complete  $\geq 36$  minutes of assigned activities on  $\geq 30$  of the 36 therapy sessions over no more than 8 weeks. Analyses will be performed using SAS and R software.

Logistic regression will be used to create a propensity score for treatment group using age, time from stroke to randomization, and total hours of outside rehabilitation therapy from Visit 1 to Visit 4 (or Visit 3 when change is to visit 3). Inverse weights based on this score will be used in secondary analyses to compute adjusted change distributions and corresponding p values. The primary analyses will be based on the inverse propensity score weighted (adjusted) change from base. The corresponding unadjusted changes will also be reported as a secondary analysis. Since this is a randomized trial, we expected the primary propensity adjusted and unadjusted results to be similar.

**Aim 1. TR+UC is superior to UC alone:** A 6-week program of TR targeting arm movement added to UC will result in better arm function as compared to UC alone. The primary endpoint is the change in ARAT score from baseline to 1 month after end of therapy (Visit 4).

The mean differences in ARAT score change from Visit 1 (baseline) to Visit 4 (1 month after end of therapy) will be compared on the log scale using an inverse propensity adjusted t test. A similar method will be used for the secondary change from Visit 1 to Visit 3 (end of therapy). We will first compare the combined TR + UC groups versus the UC group (Aim 1) and then compare TR+Sinemet+UC versus TR+placebo+UC under this model. (Aim 2). As a secondary analysis, we will report the corresponding unadjusted results.

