The difference in ARAT score change between [1] the combined TR group and [2] the UC group will be computed and the distributions compared using ANCOVA, adjusting for Visit 1 ARAT score and propensity score. Specifically, this Aim will compare UC vs. the combined two TR groups (TR+Sinemet plus TR+placebo).

Exploratory analyses will examine whether aphasia or neglect affect TR efficacy by determining if the extent of aphasia (Visit 1 LAST score) or neglect (Visit 1 SCT score), respectively, is correlated with change in ARAT score from Visit 1 to Visit 4. We will use a linear regression model with ARAT change as the outcome, and with treatment group, LAST score, and propensity score as predictors in order to assess the association. This will be repeated using SCT score instead of LAST score. Restricted cubic splines will be used to determine whether the relationships of language screening and neglect to ARAT score change are each linear.

An additional exploratory analysis will examine whether results vary according to the actual TR dose (the total number of arm repetitions across the 36 treatment sessions), using similar regression methods. Sex will also be explored: while females may have poorer functional outcomes after stroke, it is unclear whether the same underlying factors predict that sex will also be associated with a poorer response to rehabilitation therapy.

Analyses will be repeated examining a secondary endpoint, BBT, and then using several tertiary endpoints (FMA-UE, CES-D, mRS, NHPT, SIS-ADL, and SIS-hand). The lead secondary endpoint is the BBT, and this will be analyzed using alpha=0.05. The tertiary endpoints are considered exploratory and will be examined without correction for multiple comparisons. The same statistical methods as above will be used except that the dependent measure will be change from Visit 1 to Visit 4 in each of the secondary/tertiary endpoints. An additional analysis will examine mRS as the dependent variable but instead using a shift analysis (ordinal logistic repeated measures regression) of mRS change score from Visit 1 to Visits 3 and 4.

To aid in the interpretation of the above analyses, additional corollary analyses will repeat above but use as the dependent measure change from Visit 1 to Visit 3. This will be done for the ARAT as well as for the FMA-UE, BBT, mRS, and SIS-hand subsection.

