**Aim 2. TR+Sinemet is superior to TR+placebo:** Among patients randomized to TR, gains in arm function will be greater in those who take Sinemet (25/100) prior to daily TR, as compared to patients who take placebo prior to TR.

The above analyses will be repeated but instead comparing patients randomized to [1] TR+Sinemet vs. [2] TR+placebo.

**Aim 3. Less CST injury and higher dopamine polygene score predict better recovery of arm function:** Across all subjects, change in arm function will be highest in those with lower % CST injury and in those with higher dopamine polygene scores. These relationships will remain significant when examining only patients randomized to TR. The drug X gene score interaction term will be significant such that the slope of arm gains in relation to the polygene score will be smaller (less steep) in those receiving Sinemet.

**H3A:** Using linear regression, we will test whether lower % CST injury predicts higher change in ARAT score from Visit 1 to Visit 4, after controlling for baseline ARAT score and clinical measures (age, time from stroke to randomization, and total hours of outside rehabilitation therapy from Visit 1 to Visit 4). Primary analysis will examine all enrollees. Secondary analysis will examine this relationship separately for patients randomized to one of the two TR groups, while tertiary analysis will examine this separately across all three treatment groups.

Restricted cubic splines will be used to determine if the effect of continuous covariates such as age are linear. A linear model that includes individual clinical measures will be used rather than propensity adjustment so that the effect of % CST injury can be compared to the effects of the other covariates. This approach also allows us to test the hypothesis that % CST injury predicts ARAT gains beyond what can be learned from clinical variables alone.

**H3B:** We will test whether higher dopamine polygene score predicts higher change in ARAT score from Visit 1 to Visit 4, after controlling for the same covariates as in H3A. Analyses will follow those described in H3A.

Secondary analysis will repeat H3A and H3B using change in BBT from Visit 1 to Visit 4 as the dependent measure. Tertiary analyses will repeat these methods focusing on change in FMA-UE, CES-D, mRS, NHPT, SIS-ADL, and SIS-hand scores.

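### Only the Aim 1 ARAT test is powered, yet Aim 2 and the Box & Blocks Test (BBT) can each be declared significant at 0.05 whatever that test shows, and the plan does not say what such a result would establish

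*Combined protocol and SAP*

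**What the plan says.** The Sample Size section states "The primary endpoint is the ARAT, the MCID for which is 5.7 points" and "This study is powered for the Aim 1 analyses". It adds that "using a 2-sided alpha of 0.05, this study will have 80% power to detect a mean difference between groups of 5.7 points", with 72 patients allocated 27, 27 and 18.

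The Statistical Analysis section puts the primary endpoint (ARAT change, Visit 1 to Visit 4) under Aim 1. It compares combined TR with UC "and then compare TR+Sinemet+UC versus TR+placebo+UC under this model". Aim 2 is headed as a superiority claim, and its method is one sentence: "The above analyses will be repeated but instead comparing patients randomized to [1] TR+Sinemet vs. [2] TR+placebo". That carries both ARAT and BBT into Aim 2.

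On the other endpoints, the Aim 1 text says "The lead secondary endpoint is the BBT, and this will be analyzed using alpha=0.05" and "The tertiary endpoints are considered exploratory and will be examined without correction for multiple comparisons".

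No section makes one test depend on another, divides alpha, states an error rate across tests, or says how a mixed result is to be read.

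**The concern.** Four tests sit outside the exploratory label: ARAT and BBT, each for Aim 1 and for Aim 2. An alpha of 0.05 is explicit for Aim 1 ARAT and for BBT. For Aim 2 it is implied, because the Aim 1 analyses are repeated and no other level is given. The plan puts the two ARAT comparisons in order but attaches no significance condition, so the order is one of computation and not a gate.

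A null Aim 1 ARAT result followed by a significant Aim 2 or BBT result could therefore be reported as an aim met. The plan has no rule for deciding whether such a finding is confirmatory or only nominal.

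**Working it through.** **Inputs.** From Sample Size: difference 5.7, SD 7.4, two-sided alpha 0.05, groups of 27, 27 and 18. From Statistical Analysis: four tests outside the exploratory label. Assumed, because the documents do not give it: the ARAT-BBT correlation ρ, taken over the range 0 to 1.

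**1. The plan's own figure.** For 54 against 18, SE = 7.4 × √(1/54 + 1/18) = 2.014, and 5.7 / 2.014 = 2.83. Normal-approximation power is Φ(2.83 − 1.96) = 80.8%; the noncentral t gives 79.7%. The stated 80% is reproduced. For Aim 2, 1/27 + 1/27 equals 1/54 + 1/18, so the SE is the same. Power there for 5.7 points is 79.3% (noncentral t), although the plan makes no power claim for Aim 2.

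**2. The two aims are uncorrelated.** With equal TR arms the combined TR mean is (S + P)/2. Its covariance with S − P is (σ²/27 − σ²/27)/2 = 0. The UC patients are separate. Combined TR against UC and Sinemet against placebo can therefore be treated as independent.

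**3. Two ARAT tests, neither treatment effective.** 1 − 0.95² = 9.75%. No correlation assumption is needed.

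**4. All four tests.** Let p(ρ) be the chance that ARAT or BBT rejects within one aim (bivariate normal). Across both aims the chance is 1 − (1 − p)². The benefit columns count only rejections that favour the active treatment.

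| ρ | p, either direction | four tests, either direction | four tests, benefit only |
|---|---|---|---|
| 0 | 9.75% | 18.5% | 9.6% |
| 0.5 | 9.07% | 17.3% | 8.9% |
| 0.7 | 8.35% | 16.0% | 8.2% |
| 0.9 | 7.04% | 13.6% | 6.9% |
| 1 | 5.00% | 9.75% | 4.9% |

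One test alone gives 5% in either direction and 2.5% for benefit.

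**5. Check by simulation.** t tests at 27/27/18, with 200,000 runs for each ρ, gave 17.3% at ρ = 0.5 and 16.1% at ρ = 0.7 in either direction, and 8.9% and 8.2% for benefit. The two ARAT tests alone gave 9.6% to 9.8%.

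**6. Effect of the remedies, neither treatment effective.**
- Gating BBT on ARAT within each aim, with Aim 2 ungated: 1 − 0.95² = 9.75%.
- Also gating Aim 2 ARAT on Aim 1 ARAT: 5.0%, because nothing can be rejected unless Aim 1 ARAT is.
- Splitting alpha to 0.025 per aim instead: Aim 1 power falls to about 72% (normal) or 70% (t).

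**7. Price of gating Aim 2.** If both true effects are 5.7 points and the SD is 7.4 for each comparison, Aim 2 is confirmed with probability 0.797 × 0.793 = 0.63, against 0.79 ungated.

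**The case against.** Much of a hierarchy is already written. One primary endpoint is named, under Aim 1; only Aim 1 is powered; and BBT is called secondary. A reader might infer that BBT stands level with ARAT as a route to a positive trial, but the plan's own labels do not support that. What is missing is narrower: the status of Aim 2, and any condition on BBT's 0.05.

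A reader might also infer a chance of about 17%, or one in six, of a false efficacy claim. The documents do not support that either. The figure needs ρ of about 0.5, which they do not supply, and it counts rejections in both directions, including TR worse than UC or Sinemet worse than placebo. For benefit alone the figure at ρ = 0.5 is 8.9%.

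Nor does the plan break a promise of 5% across these tests, because it makes none. The 0.05 in Sample Size belongs to the Aim 1 comparison.

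Finally, TR and Sinemet are different interventions, so treating their tests as one error family is a judgement. Aim 3, on biomarker prediction, has further hypotheses that are not counted here. This is a fair argument against insisting on a family-wise correction. It does not remove the need to say which results are confirmatory and which are nominal.

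**Conclusion.** The point holds as a gap in the testing rules, to be corrected before the analysis. With neither treatment effective, the two-sided error is 9.75% for the two ARAT tests and 9.75% to 18.5% for all four, against 5% for one test. The chance of a false claim of benefit is about 5% to 10%, against 2.5%. Either way the inflation is roughly two to four times.

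The 9.75% for the two ARAT tests rests only on the plan's allocation and an implied 0.05 for Aim 2. The rest of the range depends on the unstated ARAT-BBT correlation. All figures assume complete data and simple t tests; the planned propensity weighting and multiple imputation are not modelled.

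**What to change.** In Sample Size and Statistical Analysis:

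1. Name Aim 1 ARAT change (Visit 1 to Visit 4, combined TR against UC) as the sole primary test, at two-sided 0.05.
2. Replace the BBT sentence: within an aim, BBT is tested at two-sided 0.05 only if that aim's ARAT test is significant. Otherwise it is descriptive, with an estimate and 95% CI.
3. Choose one status for Aim 2. Either test Aim 2 ARAT only if Aim 1 ARAT is significant, or label Aim 2 a secondary aim whose nominal p values cannot establish efficacy on their own.
4. Do not place Aim 1 BBT behind Aim 2. If Sinemet added nothing, that order would usually strip the lead secondary endpoint of confirmatory status even when TR works.

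One limit should be stated. If Aim 2 is gated and TR truly improves ARAT, Aim 1 BBT and Aim 2 ARAT are both open at 0.05, so error across those two could still reach 1 − 0.95² = 9.75%. A sponsor wanting 5% in that case too could use a single sequence: Aim 1 ARAT, Aim 1 BBT, Aim 2 ARAT, Aim 2 BBT. Aim 2 would then also depend on Aim 1 BBT.

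Cost: wording only, with no extra patients or data, and Aim 1 power stays at about 80%. BBT loses confirmatory status when ARAT fails. If Aim 2 is gated on Aim 1 ARAT and both true effects are 5.7 points, Aim 2 is confirmed about 63% of the time rather than 79%. Estimates and intervals are reported in every case.

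### Read literally, the ANCOVA and Aim 3 regressions for BBT and the tertiary endpoints adjust for Visit 1 ARAT and never for the endpoint's own baseline

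*Combined protocol and SAP*

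**What the plan says.** All references are to Statistical Analysis in the combined protocol and SAP, unless another section is named.

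- **Aims 1 and 2, weighted test.** ARAT change is to be "compared on the log scale using an inverse propensity adjusted t test". The section also states: "The primary analyses will be based on the inverse propensity score weighted (adjusted) change from base". The propensity model holds age, time from stroke to randomization and outside therapy hours. It holds no baseline outcome score.
- **Aims 1 and 2, ANCOVA.** ARAT change is also compared between groups by "ANCOVA, adjusting for Visit 1 ARAT score and propensity score". Aim 2 repeats the Aim 1 analyses for the two TR arms.
- **Other endpoints.** For BBT (lead secondary, alpha 0.05) and FMA-UE, CES-D, mRS, NHPT, SIS-ADL and SIS-hand (tertiary, exploratory), the rule is that the methods already described "will be used except that the dependent measure will be change from Visit 1 to Visit 4" in each endpoint. Some endpoints are then repeated for change to Visit 3.
- **Aim 3.** H3A and H3B control for baseline ARAT and clinical measures. Then: "Secondary analysis will repeat H3A and H3B using change in BBT from Visit 1 to Visit 4 as the dependent measure". The tertiary endpoints follow in the same way.

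No sentence puts an endpoint's own baseline in place of ARAT.

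**The concern.** The rule for the further endpoints names one exception, the dependent measure. Everything else carries over, including the covariate phrase "adjusting for Visit 1 ARAT score and propensity score". For ARAT that covariate is the outcome's own baseline. For BBT or FMA-UE it is a different scale.

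A change score usually depends on where the patient started on the same scale. If that starting value is left out, its variation stays in the residual and a chance group difference in it passes into the estimate. ARAT removes this only so far as it correlates with that baseline. With 18 patients planned for UC, chance differences are not negligible.

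The scores needed are already collected before randomization: BBT under Enrollment and Inclusion Criteria, CES-D under Enrollment, and FMA-UE, mRS and NHPT under Baseline Assessments.

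**Working it through.** **1. The plan's own figure.** Sample Size gives a difference of 5.7, SD 7.4, two-sided alpha 0.05, and 54 TR against 18 UC.

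- SE = 7.4 × √(1/54 + 1/18) = 2.014, and 5.7 / 2.014 = 2.83.
- Power = Φ(2.83 − 1.96) = 0.808 by the normal approximation, and 0.797 by the noncentral t.

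The total of 72 is reproduced, and this point does not change it.

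**2. Precision.** Let B be the endpoint's own baseline (SD scaled to 1) and Y its follow-up (SD s). Let ρ = corr(B, Y) and r = corr(Visit 1 ARAT, B). Assume ARAT relates to Y only through B. The residual variance of the change is:

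- adjusted for own baseline: s²(1 − ρ²)
- adjusted for ARAT: s² + 1 − 2ρs − r²(ρs − 1)²

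The SE ratio is the square root of the second over the first. The documents give none of s, ρ or r, so these are assumed values:

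| s | ρ | r = 0.3 | r = 0.5 | r = 0.7 | r = 0.9 |
|---|---|---|---|---|---|
| 1 | 0.3 | 1.221 | 1.185 | 1.129 | 1.050 |
| 1 | 0.5 | 1.142 | 1.118 | 1.082 | 1.031 |
| 1 | 0.7 | 1.077 | 1.064 | 1.044 | 1.017 |
| 1.5 | 0.7 | 1.001 | 1.001 | 1.001 | 1.000 |
| 2 | 0.5 | 1.000 | 1.000 | 1.000 | 1.000 |
| 2 | 0.9 | 1.329 | 1.277 | 1.196 | 1.077 |

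Over the whole grid (s 1 to 2, ρ and r 0.3 to 0.9) the ratio runs from 1.00 to 1.33. If own-baseline ANCOVA had 80% power, ARAT adjustment would give 69% to 78% at s = 1, ρ = 0.5, and 56% to 80% over the grid. The loss vanishes when the slope of change on own baseline, ρs − 1, is zero.

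**3. What the pilot allows.** The early-stroke pilot in Background (n = 11, end of 6 weeks) gives baseline and change SDs.

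- *FMA-UE, 5.4 and 10.3.* Squared ratio (10.3/5.4)² = 3.638. Equal SDs would need 2(1 − ρ) = 3.638, so ρ = −0.82, which is implausible. Solving s² − 2ρs + 1 = 3.638 instead gives s = 2.20 at ρ = 0.5 and s = 1.95 at ρ = 0.3. Variance inflation, for r from 0.7 down to 0, is then 0.1% to 0.3% and 2.5% to 5%.
- *BBT, 9.6 and 8.4.* Squared ratio (8.4/9.6)² = 0.766. Equal SDs imply ρ = 1 − 0.766/2 = 0.62. Variance inflation is then 12% to 24% for r from 0.7 to 0, which is about 6% to 11% in SE (√1.12 and √1.24). At ρ = 0.7 the variance figure is about 2% to 3%; at lower ρ it is larger.

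**4. Chance imbalance.** With the pilot BBT SD, the SE of the baseline difference is 9.6 × √(1/54 + 1/18) = 2.6 blocks. For Aim 2 (27 against 27) it is also 2.6. With an assumed slope of −0.5, a one-SE imbalance moves the unadjusted difference in change by 1.3 blocks. ARAT adjustment leaves a share 1 − r² of this: 91% at r = 0.3, 75% at 0.5, 51% at 0.7 and 19% at 0.9. At r = 0.7 that is 0.51 × 1.3 = 0.67 blocks.

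**5. SIS and CES-D.** Under Schedule of Events (footnotes) and Week 2 additional assessments, SIS is first scored within 5 days of discharge home or in week 2, and in UC explicitly after randomization. It has no Visit 1 value. CES-D has a screening value but is not in the Visit 4 assessment list. That should be confirmed against the schedule table.

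**The case against.** **The authors may mean the matching baseline.** ARAT's model uses ARAT's baseline, so the same method for BBT can fairly be read as using BBT's baseline. This stands as a possible intention. However, the same section says so when a covariate changes: SCT replaces LAST in the neglect analysis, and the therapy-hours window shortens when the outcome is at Visit 3. At best the covariate is left open for an endpoint tested at 0.05.

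**The analysis labelled primary is a different one.** This stands. The weighted t test has no baseline score for any endpoint, ARAT included, and rewording the ANCOVA covariate leaves it unchanged. In Aims 1 and 2 the point concerns the ANCOVA only. Aim 3 uses covariate regression instead of propensity adjustment.

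**Stronger readings the documents do not support.** A reader might infer that the Aim 1 and 2 estimates are biased, or that baseline imbalance goes wholly uncorrected. Randomization keeps the contrast unbiased on average, its standard error already reflects this variation, and ARAT removes a share r² of the imbalance. A reader might also infer that the Aim 3 slopes are confounded. That is contestable: an inherited polygene score cannot be caused by baseline BBT, and CST injury plausibly causes baseline BBT, so conditioning on it is partly a choice of estimand. The argument for own baseline is that H3A aims to show prediction beyond clinical variables, and the endpoint's own starting score is an obvious one.

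**A large loss is not established.** It depends on assumed SDs and correlations, and the pilot FMA-UE figures are compatible with almost none.

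**Conclusion.** The point holds as a defect of specification with a modest cost. Taken literally, the Aim 1 and 2 ANCOVA and the H3A/H3B regressions adjust every further endpoint for Visit 1 ARAT and none for its own baseline. In Aims 1 and 2 this loses some precision and corrects chance own-baseline imbalance only in part.

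The size cannot be fixed from the documents. The 0% to 33% range in SE rests on the grid above and on ARAT acting only through the endpoint's own baseline. It is a range under assumptions and not a bound. The primary ARAT analysis and the sample size are unaffected. Apart from BBT, the endpoints concerned are exploratory.

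**What to change.** In the Aim 1 text on secondary and tertiary endpoints, and in the matching Aim 3 text, state the following:

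- For BBT, FMA-UE, mRS, NHPT and, where a follow-up value exists, CES-D, the baseline covariate is the pre-randomization score of that same endpoint. Visit 1 ARAT may be kept in addition.
- This applies to the Aim 1 and Aim 2 ANCOVA, to H3A and H3B, and to the Visit 1 to Visit 3 repeats.
- SIS-ADL and SIS-hand are outside this rule. Visit 1 ARAT stays as their covariate, and their outcome is not described as change from Visit 1.

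The cost is a few sentences, with no new data. The wording should be settled before outcome data are examined by group. Which of the weighted t test and the ANCOVA governs each endpoint is a separate question that this change does not answer.

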**The rationale for examining whether an intact corticospinal tract is needed to benefit from TR:**

Aim 3 hypothesizes that patients with milder CST injury are more likely to achieve gains in arm function. Neural repair after stroke benefits from patient stratification, as patients with stroke are a heterogeneous population, with differing capacities to respond to rehabilitation therapy. Although several potential predictors of response to a restorative therapy in patients with subacute or chronic stroke have been identified, analysis of data from patients receiving TR in the prior national trial found that clinical measures provided limited prediction of TR-related arm motor gains. Following bivariate screening of 43 baseline clinical measures from eight categories, a multivariable linear regression model predicted only 17.6% of the variance in TR-related arm motor gains ( $p<.004$ ). Other types of measurement beyond clinical data are needed to prospectively identify treatment responders.

Neuroimaging measures are excellent candidates for predicting benefit from rehabilitation after stroke. Indeed, such measures can be superior predictors compared to clinical measures. CST injury is the focus here because it is a common pathway for TR components: the mechanism of action for TR efficacy revolves around cortical plasticity from multiple circuits driving signals down the CST--and so greater CST injury would be expected to limit treatment-related behavioral gains. Five prior studies from the [name] lab support this hypothesis, each finding that % CST injury was a significant predictor, explaining 17-33% of variance in arm motor recovery during receipt of a restorative therapy in subacute or chronic stroke. Importantly, in each of these studies, % CST injury was a better predictor than age, baseline behavioral status, and total infarct volume. For example, the largest of these studies, focused on patients in the subacute phase post-stroke, found that  $\geq 75\%$  CST injury had 91.7% positive predictive value that a patient would fail to achieve a gain on the Action Research Arm Test that reached or exceeded the minimal clinically important difference (MCID) of 5.7 points for this scale. These data suggest that treatment non-responders are common and can be accurately identified at baseline based on severity of CST injury.

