The method we use for measuring % CST injury involves [1] generating in healthy subjects a canonical CST emanating from primary motor cortex using diffusion tensor imaging (DTI) tractography, [2] outlining each patient's infarct on an anatomical MRI, and [3] overlapping each infarct on top of the canonical CST tract in MNI standard stereotaxic space. Ideally, we

would like to measure the percentage of axons in each CST that is injured by stroke, but MRI resolution does not permit this. Towards this approach, the CST is divided into 16 longitudinal subsections, aiming to model the trajectory of groups of axons. Each subsection is classified as injured or not; as with axons, a subsection need only be destroyed by stroke once along its length for it to be classified as injured.

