## Enrollment

The initial steps of study enrollment are as follows:

- Provide the patient with an overview of the study and the study timeline
- Have the patient sign the ICF and the Health Insurance Portability and Accountability Act (HIPAA) Research Authorization for Release of Protected Health Information (PHI)
- Provide the patient with a copy of the Research Participant's Bill of Rights
- Gather demographic data, medical history, and contact information, from the patient, from a subsequently obtained copy of medical records, and when possible from the electronic health record
- Complete baseline screening measures to confirm study eligibility, including:
  - **Action Research Arm Test (ARAT)**
  - **Box and Blocks Test (BBT)**

**If unable to complete BBT, will examine wrist extension and finger flexion for a visible flicker** (at least trace contraction must be present for both movements)

- **Examine range of motion against gravity in the paretic shoulder and elbow**
- **3 Rehabilitation Practice Tasks**
- **Center for Epidemiologic Studies Depression Scale (CES-D, 10 questions)**
- **Montreal Cognitive Assessment (MoCA)**
- **Trail Making Test (TMT): Part A**
- **Visual Acuity Screen**
- Complete the Eligibility Checklist, which evaluates whether the patient fully meets inclusion and exclusion criteria
- If the patient is an inpatient at Cal Rehab, enter a research progress note into the electronic health record (Epic)

The Screening Visit may be broken into more than one session, as needed.

If the patient meets all of the eligibility criteria and is amenable to study participation, they will be given a Visit 1 follow-up appointment, ideally on the next day.

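### H3A has no infarct-volume term, so a significant % CST injury slope could not be told apart from an effect of lesion size

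*Combined protocol and SAP*

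**What the plan says.** Statistical Analysis, Aim 3, H3A: a linear regression of ARAT change from Visit 1 to Visit 4 on % CST injury, "after controlling for baseline ARAT score and clinical measures (age, time from stroke to randomization, and total hours of outside rehabilitation therapy" between those visits). All enrollees are analysed first, then the TR patients, then the three groups separately. The plan enters covariates one by one instead of using the propensity score, for two reasons. The CST effect can then be set against the effects of the other covariates, and the model tests whether CST injury adds to the clinical variables. Infarct volume appears in no Aim 3 model.

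Background, rationale for the CST measure: each patient's "infarct on an anatomical MRI" is outlined and laid over a tract template built from healthy subjects. The tract is split into 16 lengthwise subsections, and a subsection counts as injured if the lesion destroys it at any one point. The same rationale says of five earlier studies that % "CST injury was a better predictor than age, baseline behavioral status, and total infarct volume", and that it explained 17-33% of the variance in arm motor recovery. This rationale, and the Background text on the active ingredients of TR, treat the CST as the pathway through which TR acts.

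H3B tests the dopamine polygene score "after controlling for the same covariates as in H3A".

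**The concern.** % CST injury and infarct volume come from the same outline. Other things equal, a larger lesion has more chances to cross a tract subsection, so the two measures may well be correlated. If larger strokes also recover less, for reasons unrelated to the tract, a model without volume credits part of that effect to the CST.

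The stake is interpretation. The rationale is specific to the tract: greater CST injury should limit gains because TR works through the CST. The planned model cannot tell that statement from the simpler one that larger strokes recover less. It also leaves out the rival predictor that the Background itself names, although the plan says it wants to compare the CST effect with those of other covariates. The missing variable needs no new scan, visit or consent.

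**Working it through.** **1. The plan's own figure.** The only power statement is for Aim 1: "using a 2-sided alpha of 0.05, this study will have 80% power to detect a mean difference between groups of 5.7 points", "assuming a SD of 7.4 points", with "27 in TR+Sinemet, 27 in TR+placebo, and 18 in UC" (Sample Size). With 3:1 allocation, the UC number is (1.960 + 0.842)² × 7.4² × (1 + 1/3) / 5.7² = 17.6, so 18, and 72 in total. Power at 54 vs 18 is 80.8% (normal) or 79.7% (noncentral t). The figure reproduces. No power is stated for Aim 3, and no printed number is wrong on this point.

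**2. Inputs for H3A.** N=72, or about 58 after the 20% dropout that the plan allows for (72 × 0.8 = 57.6). Four planned covariates, two-sided alpha 0.05. Two quantities are assumptions, because the documents do not give them: the CST-volume correlation ρ (0.3 to 0.7), and the share of variance in ARAT change that volume explains, R²v (0.05 to 0.20). Both are taken as conditional on the planned covariates.

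**3. How often the slope is significant if CST injury has no effect of its own given volume.** The induced partial correlation is r = ρ√R²v. Put f² = r²/(1 − r²) and use a noncentral F test with noncentrality N·f² and N − 6 degrees of freedom. Example: ρ=0.5, R²v=0.10 gives r² = 0.25 × 0.10 = 0.025, f² = 0.0256, noncentrality 72 × 0.0256 = 1.85, and a rejection rate of 26.8%.

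| ρ | N=72, R²v 0.05 / 0.10 / 0.20 | N=58, R²v 0.05 / 0.10 / 0.20 |
|---|---|---|
| 0.3 | 8.7% / 12.5% / 20.5% | 7.9% / 11.0% / 17.3% |
| 0.5 | 15.6% / 26.8% / 48.3% | 13.4% / 22.4% / 40.3% |
| 0.7 | 26.3% / 47.5% / 78.7% | 22.0% / 39.6% / 69.3% |

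Simulation at N=72 (20,000 runs) gave 25.4% for ρ=0.5, R²v=0.10 and 75.8% for ρ=0.7, R²v=0.20, close to the formula. With volume in the model, the rates were 5.1% and 5.0%.

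**4. How plausible that scenario is.** With no direct effect, the variance CST injury explains is ρ²R²v. This runs from 0.09 × 0.05 = 0.5% to 0.49 × 0.20 = 9.8%, and it can never exceed what volume explains. The Background reports 17-33%, with CST injury ahead of volume. Those were other cohorts, but the only evidence in the documents points away from a pure lesion-size explanation.

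**5. Cost of adding volume.** Take a CST partial R² of 0.17, the low end of the reported range, and let volume have no effect of its own. Then f² = 0.17/0.83 = 0.205, and noncentrality at N=72 is 14.7 before adjustment and 14.7 × (1 − ρ²) after it.

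| N | planned model | with volume, ρ 0.3 / 0.5 / 0.7 |
|---|---|---|
| 72 | 96.6% | 95.0% / 90.6% / 77.1% |
| 58 | 92.3% | 89.7% / 83.4% / 67.5% |

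At a partial R² of 0.33, power stays at 96% or above in every case.

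**The case against.** The strongest reply is that Aim 3 is about prediction. The Study Overview speaks of predictive value and of finding responders in advance, and H3A's stated target is prediction beyond clinical variables. Infarct volume is an imaging variable, and a predictor need not be causal. This stands: the percentages in step 3 are not type I errors for the hypothesis as the plan words it. They bear only on the tract-specific reading.

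Three further replies stand in part. The dependence on lesion size is not complete: a small infarct across the tract can score high and a large one elsewhere can score zero, so correlations of 0.6-0.7 are unsupported. Baseline ARAT, already in the model, may absorb some of the lesion-size effect. And adjustment can cost real power, more so because patients who cannot have an MRI may still be enrolled (MRI Screen). None of these is a reason to leave the comparison out. They are reasons to report both models.

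A reader might extend the point to H3B and infer that ancestry is a comparable omitted confounder, available from data already held. The documents do not support that. Enrollment says only "Gather demographic data, medical history, and contact information", without naming race or ethnicity. Genetic Testing does not state how broad the genotyping is, and the five polymorphisms in the score cannot estimate ancestry. On assumed shifts between two strata (40% in one) of 0.3/0.2, 0.5/0.3 and 1.0/0.5 SD in score/ARAT change, the rejection rate at N=72 is 5.4%, 6.3% and 14.0%. Nor would a race or ethnicity main effect repair the drug x gene model: drug is randomized, so ancestry biases that interaction only if it modifies the drug effect.

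**Conclusion.** The point holds for H3A and for interpretation only. As planned, a significant % CST slope is a valid prediction beyond the four listed covariates, but it does not separate tract injury from lesion size, which the Background's argument requires. A reader might infer that a positive Aim 3 would be spurious or would fail to support the biomarker. That goes too far: it needs a scenario with no direct CST effect, which the Background's reported results point against.

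The size of the confounding is unknown. Over the assumed grid at N=72, the slope would be significant in 9% to 79% of trials with no direct effect. The width of that range shows how much rests on two quantities that the documents do not give. The change is worth making because it is specific, cheap and settles the question from data already processed.

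**What to change.** Keep the H3A model as written. Before the data are analysed, prespecify a companion model that adds total infarct volume on the log scale, computed from the same lesion mask. Report the % CST injury slope and its confidence interval from both models. State in the SAP that any tract-specific conclusion is limited to what the volume-adjusted model supports, while the planned model answers the question about prediction beyond clinical variables.

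The cost is SAP wording, one degree of freedom and a wider interval in the companion model, with the power losses shown above. If the two measures prove highly correlated, the adjusted interval may be too wide to decide between them. The report should then say so rather than read a non-significant adjusted slope as evidence against the tract.

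For H3B, at most an optional sensitivity analysis, if the sponsor confirms that race/ethnicity or ancestry markers are recorded. It should not be presented as a remedy for the drug x gene interaction.
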